#### 1 Introduction

#### 1.1 Background – fatigue after critical illness

Patients experiencing acute illness will often have a prolonged recovery time. The cause of this is unknown, but certain factors, like age, duration and graveness of the illness, is associated with prolonged recovery. ICU-acquired weakness negatively impacts prognosis and in one study, 122 patients with ICU-acquired weakness was matched to non-weak controls and the one-year mortality was found to be almost twice as high in the weakness group.

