#### Project design, method selection and analyses

To ensure the best possible validity, we have decided to go for a randomized placebo-controlled study design with double blinding. In addition to a pilot phase with four-six patients which has started the study will have four phases with 16-26 randomized patients each, firstly into a low dosage group (250mg x1) and then the same number of patients into progressively higher dosage groups (250mg x2, 250mg x4 and 250 mg x8) in the next phases (Figure 8). Patient will be treated with the study drug for three months to ensure coverage over the whole recovery period for most patients.

Some unevenness in the randomization is likely given the relatively small number of patients and because patients in ICUs are a very heterogeneous group. The relatively strict exclusion criteria will on the other hand make the participants more homogenous.

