| Hearing Assessment **  | At baseline, day 7, day 90 and week 65.                                 |
|  |   |
| SAPS2 (Filled in by investigator).                               | On admission to ICU or first day at hospital for patients never at ICU. |

(\*) Portable audiometry, tympanometry and otoscopy.

- 2: EQ5D.
- 3: Forward-backward recall.
- 4: Trailmaking A.
- 5: 4 meter walking test.
- 6: Trailmaking B.
- 7: MOCA
- 8: Hearing assessment.

(\*\*) Patient's level of fitness will vary considerably and individual evaluations will be made for all patients regarding their ability to complete all or some of these assessments. For patients who are capable of competing all individual tests, but for whom the sum of the assessments is too large, the assessments should for the most part be prioritized as follows:1: Grip strength.

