2.3 Sample size

Assuming the time of hospitalization after randomization follows a Weibull distribution with a scale parameter λ = 18 and shape parameter κ =2.2 (corresponding to a median of 15 and an IQR of 10 – 21), we need to include 58 patients: 18 in the placebo group, 10 in the 250 mg/day group, 10 in the 500 mg/day group, and 20 in the 1 g/day group) in order to reach approximately 80% power to show a significant dose-response in this study with a maximal reduction in time of hospitalization of 33%. This calculation is based on optimal designs in dose-finding studies according to the MCPMod methodology with three alternative dose-response curves: linear, e-max and exponential (Pinheiro et al., 2014).

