2.4 Statistical Framework

The statistical framework will be based on the context of dose-finding, for which there are two main approaches: "regression" and "contrast" (Senn, 2007). In the regression approach, the actual doses used in the trial are viewed as samples from a dose continuum, and the purpose is to estimate the dose response curve. In the contrast approach, interest is on one or (more likely) several contrasts between the doses used in the trial. The former is the most explorative and may be sensitive to modeling choices, small number of doses, and over-fitting, especially for small sample sizes (such as in this trial). The latter is well suited for determining the *minimum effective dose*, in which we compare the different doses to placebo.

Specification of the Primary Objective

The primary objective of this study will be to establish the minimum effective dose of NR on shortening recovery time after critical illness. The primary outcome is length of hospital stay in days (see Section 5.1 for details).

There is only one identified primary analysis in this trial. All other efficacy analyses will be regarded as supportive or exploratory.

Hypothesis Setup

Let μ_1 , μ_2 , μ_3 , and μ_4 denote the mean lengths of hospital stay for placebo, low dose (250 mg/day), medium dose (500 mg/day), and normal dose (1 g/day), respectively.

The statistical scheme to account for multiple testing is based on the *closed multiple test procedure* of Marcus et al. (1976). Under the monotonicity assumption, we define a set of elementary null hypotheses (the many-one comparison) with a preassigned order of performing the tests (Williams, 1971):

Step 1: Test the null hypothesis H_0 : $\mu_1 = \mu_4$ Step 2: Test the null hypothesis H_0 : $\mu_1 = \mu_3$ Step 3: Test the null hypothesis H_0 : $\mu_1 = \mu_2$

The test in Step 1 is carried out with a nominal significance level of α = 0.05. If the test is rejected, the test in Step 2 can be carried out, also with α = 0.05. If the test in Step 2 is rejected, the test in Step 3 can be carried out (with α = 0.05). The tests in steps 2 and 3 are only performed if the preceding null hypothesis is rejected, which – together with the monotonicity assumption – ensures that the significance level is preserved for the entire procedure (Williams, 1971; Bauer, 1991). All tests will be performed two-sided.

Decision Rule

The testing scheme above can result in four situations:

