6.1 Primary Outcome

The primary outcome is length of hospital stay (time to discharge), measured in number of days, and the primary analysis of the primary outcome will be performed on the full analysis set (FAS). A secondary (sensitivity) analysis of the primary outcome will be performed on the per protocol set (PPS).

Statistical Method for Steps 1-3

The comparison of the length of hospital stay between the NR and placebo groups – in each of the three steps – will be carried out with a Weibull survival model, with time as the number of days of hospital stay and treatment (NR vs placebo) as explanatory variable. The estimated treatment effect will be the hazard ratio (HR) for treatment with a 95% confidence interval.

Presentation of Results

The estimated treatment effect (HR) with a 95% confidence interval will be presented, together with the P-value for the null hypothesis of a zero-treatment difference (HR = 1).

The observed mean and standard deviation for placebo and each dose will be presented in a figure, along with the observed values (length of hospital stay) for each individual, as a scatter with connected lines-plot. Figure 1 shows an example with simulated data.

A plot of the Kaplan-Meier survivor function (for time to discharge) of each dose and placebo will be presented.

[figure not shown]

Figure 1: Simulated data

Missing Data

We will have complete data on the length of hospital stay, except for the following situation: A patient dies before being discharged from the hospital. In this case, the patient will be censored at the time of death. Imputation of the length of hospital stay will be performed as a sensitivity analyses (see item 3 below).

Sensitivity Analyses

The following sensitivity analyses will be performed on the primary outcome:

- 1. As described above but on the per protocol set (PPS)
- 2. As described above but with Cox proportional hazard regression instead of Weibull regression
- As described above but with Cox proportional hazard regression and imputation (instead of censoring) of the length of hospital stay with the maximum length of hospital stay (regardless of treatment group) for patients who die before discharge

Subgroup Analyses

There will be no subgroup analyses.

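### The primary Weibull model is unadjusted, although the protocol calls age and illness severity prognostic and both are recorded before treatment; pre-specifying them is a cheap improvement of unproven size

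*SAP*

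**What the plan says.** SAP 6.1 compares NR with placebo in each of the three steps by a Weibull survival model with "treatment (NR vs placebo) as explanatory variable". No other term is named. The three sensitivity analyses (per-protocol set, Cox regression, Cox regression with imputed stays for deaths) change the population, the model or the handling of deaths, but not the covariates. SAP 4.3 summarises baseline values by arm and says that important imbalance will be noted; no analysis follows from such a note.

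Protocol 1.1 states that "certain factors, like age, duration and graveness of the illness, is associated with prolonged recovery". The protocol's passage on project design says "Some unevenness in the randomization is likely given the relatively small number of patients", and gives the heterogeneity of ICU patients as a further reason. Its next sentence adds that the strict exclusion criteria work in the other direction.

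Age is among the baseline items in SAP 4.3. SAPS II is in Protocol Table 3, scored at ICU admission or on the first hospital day, so before study treatment.

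On testing, SAP 2.4 says "The test in Step 1 is carried out with a nominal significance level of α = 0.05" and "All tests will be performed two-sided". If Step 1 fails, the decision is that NR has no effect at the doses studied. SAP 2.3 assumes that stay "follows a Weibull distribution with a scale parameter λ = 18 and shape parameter κ =2.2" and claims "approximately 80% power to show a significant dose-response in this study with a maximal reduction in time of hospitalization of 33" per cent.

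**The concern.** The protocol names two prognostic factors and predicts that small groups will differ, and both factors are recorded. The primary model then uses neither. If they predict remaining stay, leaving them out wastes precision at Step 1, the gate on which the whole procedure depends.

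An illustration shows the scale. With 18 against 20 patients, a standardised covariate differs between arms by more than 0.5 SD with probability about 12% (SE of the difference √(1/18 + 1/20) = 0.325; 0.5/0.325 = 1.54). With 18 against 10 the probability is about 20%. The SD of log stay under the planning Weibull is π/(√6 × 2.2) = 0.583. If the covariate explained 20% of that variance (an assumption), a 0.5 SD imbalance would shift mean log stay by 0.5 × √0.2 × 0.583 = 0.13. That is about a third of the planned effect, ln 0.67 = −0.40.

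**Working it through.** **Inputs.** From SAP 2.3: Weibull with scale 18 and shape κ = 2.2; 18 placebo, 10, 10 and 20 patients; maximal reduction 33%, so time ratio 0.67. From SAP 2.4: two-sided α = 0.05 per step. Assumed: no deaths before discharge, so 38 events in Step 1. Assumed: R², the share of log-stay variance explained by baseline. The documents give no value, so 0 to 30% is shown.

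**The plan's own figure.** A maximum-contrast MCPMod test on log time (group variance 1/(nκ²), one-sided 0.025), averaged over linear, e-max and exponential curves, gives 78.7% to 80.2%. This range covers assumed ED50 values of 50 to 500 mg and exponential parameters of 200 to 1,000 mg. The stated 80% reproduces, but for a dose-response test and not for the stepwise Weibull comparisons in SAP 6.1.

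**Planned Step 1, unadjusted.** Discharge HR = 0.67^(−2.2) = 2.41, log HR = 0.881. SE = √(1/18 + 1/20) = 0.325. Power = Φ(0.881/0.325 − 1.96) = 77.4%.

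**Adjusted, with stay marginally Weibull as planned.** The unadjusted model is then correctly specified and stays at 77.4%. With the time ratio fixed at 0.67, the conditional shape becomes 2.2/√(1 − R²):

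| R² | shape | log HR | Step 1 power | gain |
|---|---|---|---|---|
| 0.1 | 2.32 | 0.929 | 81.6% | 4 |
| 0.2 | 2.46 | 0.985 | 85.8% | 8 |
| 0.3 | 2.63 | 1.053 | 90.0% | 13 |

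**Adjusted, holding only the log-time variance.** Weibull regressions were simulated (2,000 or 3,000 trials per setting, 18 against 20, no censoring, Wald test). Entries are unadjusted → adjusted power in %:

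| R² | two covariates, 2,000 trials | two covariates, 3,000 trials | one covariate, 3,000 trials | one covariate, second set of 3,000 |
|---|---|---|---|---|
| 0 | 79 → 76 | 78.6 → 75.9 | 78.1 → 77.6 | cost about 2 |
| 0.1 | 73 → 79 | 74.9 → 79.3 | 73.8 → 81.2 | 73 → 79 |
| 0.2 | 70 → 84 | 71.1 → 84.1 | 72.7 → 85.3 | 70 → 84 |
| 0.3 | 68 → 87 | 67.6 → 88.1 | 67.9 → 88.5 | 65 → 88 |

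The gains are about 6 points (4 to 7 across runs), about 14 (13 to 14) and 19 to 23. They exceed the formula's because stay is no longer marginally Weibull here, so the unadjusted model also loses power. At R² = 0, two covariates cost 2.7 to 3.5 points (the last set gave 3.5). Four covariates cost 78.3 − 73.5 = 4.8.

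**Type I error.** At R² = 0 the unadjusted Wald test already rejects in 7% to 8% of null trials in the 3,000-trial runs. With two covariates, unadjusted against adjusted, it is 8.0% against 8.2% at R² = 0 and 8.9% against 7.8% at R² = 0.2. With size-corrected tests the comparison has the same direction: 72.2% against 68.6% at R² = 0, and 60.7% against 78.1% at R² = 0.2.

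**Steps 2 and 3.** SE = √(1/18 + 1/10) = 0.394. Even if each dose gave the full 33%, power is Φ(0.881/0.394 − 1.96) = 60.8% for each step alone. Allowing for the shared placebo group, the chance of passing Steps 1 and 2 is 52.5% if every dose gives 33%, and 15.9% if the reduction is linear in dose. With R² = 0.3 and adjustment, the linear case rises only to 21.9%.

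**The case against.** An unadjusted primary analysis with 28 to 38 patients per step is defensible. The protocol says only that age and severity are associated with slower recovery. SAPS II describes the patient at admission, whereas the outcome clock starts at study treatment, once the patient is medically stable and expected to stay at least 7 more days (Protocol 4.3). How well an admission score predicts remaining stay in that selected group is unknown, and strict exclusions may weaken the relation. All of this stands; it is why the gain is given as a range that includes a loss.

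Three stronger readings are tempting, and the documents do not support them.

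- A reader might infer that a known, large amount of power is being given away. No figure in either document shows that the covariates are strongly prognostic, and neither links the Clinical Frailty score or Charlson index to length of stay. Under the plan's own marginal Weibull assumption the gain is the smaller set of figures.
- A reader might infer that the unadjusted hazard ratio is biased or its test invalid for want of covariates. The hazard ratio is non-collapsible: the marginal and conditional values are different targets, each legitimate. Chance imbalance is part of the sampling error of a randomised comparison. The excess type I error is present at R² = 0, and adjustment does not restore 5%.
- A reader might infer that adjustment would make the trial adequately powered. Step 1 is only slightly short at a 33% reduction (77.4%). The real shortage is in Steps 2 and 3, and at smaller effects (49.5% in Step 1 for a 25% reduction); adjustment narrows it but does not close it.

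**Conclusion.** The point holds as a cheap improvement, not as an error. The primary model and all its sensitivity analyses omit two factors that the protocol itself calls prognostic and that are recorded before treatment. The expected balance favours adjusting: about 3 points of Step 1 power lost if the two covariates carry no information, against 4 to 13 points gained by formula, or about 6 to 23 in the variance-matched simulations, if they explain 10% to 30% of log-stay variance. These sizes rest on the assumed R², a 33% reduction, linear covariate effects and no deaths before discharge. The direction does not depend on which of the two calculations is preferred, provided the covariates explain roughly 10% or more.

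**What to change.** Before unblinding, amend SAP 6.1 as follows.

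- Include age and SAPS II as linear terms in the Weibull model for Steps 1 to 3 and in the Cox sensitivity models. The per-protocol analysis then follows the same model.
- Use no more than these two. In particular, take no post-randomisation item from the SAP 4.3 list, which includes mortality and new organ failures.
- State that the treatment effect is then the hazard ratio conditional on age and SAPS II.
- State in advance how a missing SAPS II value is handled.
- Keep the treatment-only Weibull model as a sensitivity analysis.

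The cost is SAP wording, since both items are already in the data collection and Protocol 10.4 allows changes to the plan until database lock. The statistical price is about 3 points of Step 1 power if the covariates prove uninformative. Adjustment chosen after unblinding, in response to an imbalance that had been noted, would be post hoc.

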6.2 Secondary Continuous Outcomes (Change from Baseline)

Secondary continuous outcomes with change from baseline include grip strength at day 90 and grip strength at day 7. The analyses will be performed on the FAS.

Statistical Method for Steps 1-3

A linear mixed model will be fitted to the three measurements of grip strength (baseline, day 7, and day 90) in each step. The model will contain fixed effects for treatment (NR vs placebo), time point (day 7 vs baseline & day 90 vs baseline), and treatment x time point interaction and a random intercept. Based on the fitted model, we can estimate change from baseline to day 7 and change from baseline to day 90 in each group and the between-group difference in changes from baseline for both time points.

Presentation of Results

We will present the observed mean values and standard deviation for each group at each time point (baseline, day 7, and day 90). We also present the estimated change from baseline to day 7 and the estimated change from baseline to day 90 in each group with 95% confidence intervals, and the estimated between-group differences in changes from baseline to day 7 and to day 90 (the treatment difference), also with 95% confidence intervals.

Missing Data

Missing data on grip strength at either day 7 or day 90 will be handled by the linear mixed model, under the assumption of missing at random. There is no missing data on grip strength at baseline, so all patients will be included in the model.

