#### 10.5.2 Secondary Endpoint of Special Interest:

Change in the level of frailty measured as grip strength at inclusion, on day 7, and on day 90. Should a patient withdraw from the study, grip strength will be measured at the withdrawal visit.

Grip strength is a simple measure used to indicate overall muscle strength (34, 33). It has been shown to inhabit health-related prognostic value and evidence suggests that it is a powerful predictor of future disability, falls, morbidity and mortality (33, 35-37). Grip strength will be measured in both arms using a dynamometer. Each participant will be tested twice on both the right and left, and the highest score on either side will be registered.

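### The grip-strength model in SAP 6.2 is valid but makes no use of the randomised baseline; a common baseline mean with a phase term would gain modest precision at little cost

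*SAP*

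**What the plan says.** Protocol 10.5.2 names grip strength the secondary endpoint of special interest: "Change in the level of frailty measured as grip strength at inclusion, on day 7, and on day 90". It fills two of the five secondary rows in the SAP's table of outcomes for the main article (SAP 5).

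SAP 6.2 sets out the analysis. "A linear mixed model will be fitted to the three measurements of grip strength (baseline, day 7, and day 90) in each step". On the mean structure, "The model will contain fixed effects for treatment (NR vs placebo), time point", with day 7 and day 90 each set against baseline, is followed by "treatment x time point interaction and a random intercept". The reported effect is "the between-group difference in changes from baseline for both time points". On completeness, "There is no missing data on grip strength at baseline, so all patients will be included in the model", and "Missing data on grip strength at either day 7 or day 90 will be handled by the linear mixed model" under missing at random. Nothing sets a common baseline mean, and baseline is not a covariate.

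Three other parts of the plan matter here:
- SAP 2.4 carries out steps 2 and 3 for a secondary outcome only if the 95% interval from the step before excludes the null value.
- SAP 2.2 blocks the randomisation within each phase. SAP Table 1 in section 2.1 gives each dose to one phase only, with 6 placebo patients per phase.
- SAP 6 compares one dose group with the placebo group in each step. Read plainly, that is 18 placebo patients drawn from all three phases.

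**The concern.** With time coded against baseline, the treatment main effect is the difference between arms before the first capsule. Protocol 6.2.1 has endpoint baselines assessed before treatment starts, so within a phase randomisation makes the expected value of that difference zero. Estimating it freely discards that knowledge. The contrast reduces to change in one arm minus change in the other, with no adjustment for a chance imbalance at baseline, although weaker patients at baseline will tend to gain more through regression to the mean.

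The comparisons are small (20 v 18, then 10 v 18), and interval width does more than describe uncertainty: under SAP 2.4 it decides whether the lower doses are estimated at all. The baseline measurements that would narrow the interval are already collected and, by the SAP's own statement, complete.

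**Working it through.** **Inputs.** Placebo 18 (6 per phase); NR 20, 10 and 10 (SAP 2.1). Random intercept only, hence one correlation rho between any two visits (SAP 6.2). Neither document gives rho, a standard deviation, an effect size or a power figure for grip strength, so there is no stated figure to reproduce; the 80% in SAP 2.3 concerns length of stay. I assume rho 0.5 to 0.9. The SD cancels in the ratios, and variances below are in SD² units.

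**Planned model, complete data.** Write k = 1/n1 + 1/18, with n1 the size of the dose group. The difference in change, D, has variance 2(1-rho)k.

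**Common baseline mean, no phase term.** Fixing the baseline difference at zero lowers the variance by Cov(D,E)²/Var(E), where E is the estimated baseline difference. Here Cov(D,E) = -(1-rho)k and Var(E) = k, so the new variance is 2(1-rho)k - (1-rho)²k = (1-rho²)k. The relative cut is (1-rho)/2, the same for day 7 and day 90.

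**Common baseline mean within phase.** Add a phase main effect that is constant over time. The placebo baseline in the dose's own phase is then the three-visit mean of the 6 concurrent patients, less the average visit effect estimated from all 18. Its variance is (1+2rho)/18 + (2/3)(1-rho)/18 = (5+4rho)/54. Cov(D,E) is unchanged, so the relative cut becomes

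(1-rho)/2 x (1/n1 + 1/18) / (1/n1 + (5+4rho)/54).

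Example, rho 0.5, 20 v 18: 0.25 x 0.1056/(0.0500 + 0.1296) = 14.7%. A direct generalised-least-squares calculation gives the same values.

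| rho | planned 2(1-rho) | common mean 1-rho² | variance cut | SE cut | variance cut with phase, 20 v 18 | with phase, 10 v 18 |
|---|---|---|---|---|---|---|
| 0.5 | 1.00 | 0.75 | 25% | 13% | 14.7% | 16.9% |
| 0.7 | 0.60 | 0.51 | 15% | 8% | 8.1% | 9.5% |
| 0.8 | 0.40 | 0.36 | 10% | 5% | 5.2% | 6.2% |
| 0.9 | 0.20 | 0.19 | 5% | 2.5% | 2.5% | 3.0% |

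With phase, the SE cut for 20 v 18 is 1 - sqrt(0.853) = 7.6% at rho 0.5 and 1 - sqrt(0.975) = 1.3% at rho 0.9.

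**Departures from the ideal, common mean without phase.** If 10% were missing at day 7 and 30% at day 90 (an illustration; Protocol 10.1 calls dropout unknown), the day-90 cut would be 19%, 12% and 4% at rho 0.5, 0.7 and 0.9. With rho estimated in 10,000 simulated complete-data trials per setting, it was 25%, 15% and 5% for 20 v 18 and 22%, 12% and 3% for 10 v 18.

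**Why phase is needed.** Suppose baseline grip in the dose's phase is shifted by s SD and change is unaffected. Twelve of the 18 placebo patients come from other phases, so the expected baseline gap is d = s x 12/18. A common mean without phase is biased by (1-rho)d. With s = 0.5, d = 0.33 and the bias is 0.17 SD at rho 0.5 (SE 0.28) or 0.03 SD at rho 0.9 (SE 0.14). The planned contrast has no bias in that case. The squared bias (1-rho)²d² cancels the variance saved, (1-rho)²k, once d = sqrt(1/20 + 1/18) = 0.32 SD, that is s = about 0.49 SD, whatever rho is. For 10 v 18 the figure is s = 0.59 SD.

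**ANCOVA on baseline plus phase.** Each dose sits in one phase, so a phase term in a single-visit ANCOVA leaves only the 6 concurrent placebo patients in the contrast. Its variance is about (1-rho²)(1/n1 + 1/6). At rho 0.5 and n1 = 20 that is 0.75 x 0.2167 = 0.163, against 0.106 for the planned model. It is safe against phase shifts but loses precision.

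**The case against.** The planned contrast is a standard, unbiased estimate of the quantity that SAP 6.2 names. It uses all available visits under missing at random and improves on the t test in Protocol 10.5.4. Secondary outcomes are estimated and not tested, and SAP 2.4 classes every analysis other than the primary as supportive or exploratory. No effect size or SD is available to show that a slightly narrower interval would change whether step 2 or 3 is reached. All of this stands, and it limits the point to an improvement.

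Three stronger readings are tempting, and the documents support none of them:
- *The plan wastes 5-25% of the information.* That range is only rho 0.9-0.5 put into (1-rho)/2 with complete data. At rho 0.95 it is 2.5%, at rho 0.3 it is 35%, and the documents give no rho.
- *Randomisation makes the true baseline means equal in each comparison.* It does so within phase. Twelve of the 18 comparators in each step were not randomised against that dose.
- *A common baseline mean has no downside.* Without phase it can import bias, as shown above. Protocol 4.1 lets recruitment extend to other wards and hospitals, and liver eligibility was relaxed in November 2020, so a shift between phases is possible. Nothing shows that grip strength did shift.

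The objection disposes of a common mean without phase. It does not dispose of one with phase, which still gains precision.

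**Conclusion.** The point holds as a cheap gain in precision on the protocol's secondary endpoint of special interest. SAP 6.2 leaves the baseline difference free, so with complete data its treatment effect is the simple difference in change.

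The safe form of the alternative, with a phase term, lowers the variance by about 2.5-15% for 20 v 18 and 3-17% for 10 v 18. This rests on rho between 0.9 and 0.5, complete data, the random-intercept covariance, and any phase shift in grip being constant over time. Missing follow-up makes the gain smaller. The last assumption is hardly new: pooling placebo change over phases in the planned contrast already needs mean placebo change to be the same in each phase.

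**What to change.** Before database lock (Protocol 10.4 allows amendments to the plan until then), amend SAP 6.2 as follows:

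1. Remove the treatment main effect. Keep the two time-point effects, the treatment x time terms for day 7 and day 90, and the random intercept.
2. Add a phase main effect with three levels.
3. Keep the planned model with the free treatment main effect as a pre-specified sensitivity analysis.

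The estimated quantity stays the same: the between-group difference in change at each visit. If ANCOVA on baseline grip plus phase is preferred, the SAP should say that it rests on concurrent placebo only and, at these group sizes, widens the interval; it should not be chosen for precision.

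The cost is a sentence or two of SAP text, a net one extra parameter (two for phase, less one for treatment), and the assumption of a time-constant phase shift. No new data are needed. Phase is readable from the subject number (Protocol 5.8), so nothing has to be unblinded.
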